- 8) perform behavioral assessments, baseline and post-TMS, to study whether there are measurable changes following stimulation of the target brain region.

4) Resources: Describe the resources (personnel, facilities, time, emergency resources, etc.) available to recruit, consent, conduct study procedures, and analyze data.

Our clinical collaborators will participate in patient recruitment. MRI scans, TMS treatment, neuropsychological assessment, and assessments with body worn devices will be done at the Biosciences Research Laboratories (BSRL) at [name]. All persons assisting with the study have received appropriate training and are or will be knowledgeable in their study-related duties and functions.

[name], Assistant Professor, Cognition and Neural Systems, and her team will be involved in the neuropsychological testing as well as the TMS treatments. Her research focuses primarily on 1) characterizing the mapping between brain organization and behavior, and 2) studies of transcranial magnetic stimulation (TMS) techniques for modulation of human brain function and behavior.

5) Study Population

12 participants with PCCI will be recruited to participate in this trial.

Inclusion Criteria:

- Adult (>=18).
- PCCI diagnosis (see information below).
- Right Handed (We will not enroll left-handed dominant people because they tend to have more symmetric brain function and thus targeting the left frontal region may not be as effective.)
- English speaking.
- Cancer treatment completed and considered curative with the exception of endocrine therapy after chemotherapy.
- Able to attend daily intervention (Monday-Friday) for 2 weeks.
- Not enrolled in another interventional study within 6 months prior to beginning this study.

Exclusion Criteria:

- Pregnancy or thinking of becoming pregnant.
- Undergoing active treatment for cancer.
- Routine contraindications for MRI (including incompatible medical implants or metal fragments in the body at risk for migration or heating with application of the magnetic field) including severe claustrophobia.
- History of brain metastasis or other brain tumor.
- History of stroke or traumatic brain injury.
- Frequent or severe headaches.
- Cognitive or mood disorder prior to chemotherapy (i.e. dementia or depression).
- History of epilepsy, or other seizure disorders.
- History mental health disorders, such as substance misuse, bipolar disorder or psychosis.

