- Taking medication for seizures or that could lower seizure threshold if withdrawn.
- Inability to complete neuropsychological testing.
- Prior treatment with rTMS. We will enroll subjects without prior experience with rTMS.

PCCI Diagnosis: Given lack of universally accepted criteria, we will initially follow commonly used criteria for mild cognitive impairment (MCI). The following revised Mayo clinic criteria for MCI will be used: (a) self- or informant-reported cognitive complaint; (b) objective cognitive impairment; (c) preserved independence in functional abilities; and (d) absence of dementia. The MCI diagnosis will be supported by the measures of general cognitive function using Mini-Mental State Exam (MMSE) 24-27 points (inclusive); (2) Montreal Cognitive Assessment (MoCA) 18-26 points (inclusive); and (3) Clinical Dementia Rating Scale score of 0.5. In addition, the Jak/Bondi actuarial neuropsychological test method and NACC UDS 3.0 Neuropsychological battery will be used identify MCI (i.e., 1 standard deviation below the mean for their age and education matched peers on normative data in at least 2 memory tasks). We will not include those with unstable medical condition, contraindications to MRI and TMS, clinical evidence of stroke, psychiatric disorder, and other neurological disorders or head injury.

6) Recruitment Methods and Consenting Process

Recruitment will begin after IRB approval and other approval requirements are complete. We plan to recruit for approximately 2 years or until we have recruited and completed 12 subjects, whichever comes first.

Our Banner University Medical Center clinical collaborators will participate in patient recruitment. When the physicians are seeing cancer patients as part of their routine standard of care, potential subjects will be identified.

Pre-screening in clinic is currently envisioned to be the combination of both the patients' symptoms and physicians' assessment consistent with "chemobrain." The patient will then be asked by the oncologist or staff if they are interested in a clinical trial for the treatment of "chemobrain" or whatever terminology the oncologist feels will best describe the symptoms the patient is describing (in other words, the oncologist does not need to use the exact term

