“chemobrain”). If the patient is interested in participating, contact information will be collected on a consent to contact form and provided to the research staff. We hope that signing the consent to contact form rather than the full consent will save time and minimize disruption of the clinic’s workflow.

The research staff will contact the individuals using the consent form as a script to describe the study. During this phone conversation, the inclusion and exclusion criteria will be reviewed with the patient to verify eligibility.

The identified individuals will be given ample time to review the consent and time commitment before consenting to the project. The patient will then receive a detailed schedule of research appointments. The first appointment will include the neuropsychiatric exams and pre-determined cut-offs (previously described) will be used to select appropriate subjects. The selection is based on multiple neuropsychiatric tests.

Any information collected during this phone-screening process will be secured under lock and key to ensure confidentiality. If the participants withdraw from the study, all personal information collected will be destroyed in a shredding machine to protect confidentiality of any PHI or sensitive data that may have been recorded.

7) Consenting Process

The consent will be obtained in a private setting to preserve confidentiality. All patient questions will be answered and no procedures will be completed before consent form is signed. No undue pressure will be applied to obtain consent.

This consent process will occur with a trained member of the research staff. The Consent Form will be reviewed by both the participant and the member of the research staff. The participant will be encouraged to ask any questions that arise while reviewing the informed consent form. Upon completion of the consent form and additional oral explanation provided by the research staff, the research participant will be asked to sign the consent form and a copy will be provided to them.

Throughout this consent process, the research staff will communicate the participant’s right to withdraw from the study at any time without penalty. No minors or participants unable to consent will be included in this trial.

8) Research Procedures Involved in the Human Research

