Subjects will undergo testing at baseline prior to TMS treatments and once more at the end of the 2-week intervention. All study activities will occur at the Biosciences Research Laboratories (BRSL) Building, located at [name].

Child-bearing females will be required to take a urine pregnancy test and requested that adequate birth control be used during the treatment phase of the study.

A) Brain imaging data

We will acquire diffusion weighted imaging (DWI), resting-state fMRI, and T1 structural MRI. The MRI technician will ensure that participants have proper ear protection in the scanner (e.g., protective headphones so we can still communicate with them for the duration of the scan). The MRI technician will take measures to optimize the comfort of the participant (e.g., warm blankets, back support cushion). Foam pads will also be used to reduce head motion. Diffusion weighted MRI and resting-state functional MRI will be used to measure structural and functional connectivity, respectively. During resting-state fMRI scans, participants will be instructed to rest and remain awake with their eyes fixated on the cross hair presented before them. Total MRI scan time will require approximately 30 minutes.

B) Neuropsychological data and demographic data (see attached document: NACC UDS 3.0 Neuropsychological battery.pdf)

We will use a selection of MMSE, CDR, and NACC UDS 3.0 Neuropsychological battery. The NACC UDS Battery includes MoCA, Craft Story 21 Recall (Immediate), Benson Complex Figure Copy (Immediate), Number Span Test (Forward and Backward), Category Fluency, Trail Making Test, Craft Story 21 Recall (Delayed), Benson Complex Figure Copy (Delayed), MINT, and Verbal Fluency – Phonemic Test, to assess cognitive performance. Additionally, AVLT (Immediate Recall, Delay Recall), NAART (North American Adult Reading Test), and Stroop will also be applied for measuring cognitive function. Some of these tasks require audio recording for ease of scoring. Besides, demographics data, health history, medications, family history, and handedness questionnaire, will be collected. Acquiring neuropsychological and demographical data will take approximately 2 to 3 hours.

C) Memory tasks (see attached document: Memory tasks 20190318.docx)

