After the conclusion of baseline data acquisition, the research team will analyze each participant's unique structural and functional connectivity patterns to determine stimulation site for TMS in future study sessions.

The subjects will receive 10-sessions (1 session per day, M-F over 2 consecutive weeks). The treatment itself lasts approximately only 190 seconds but we are conservatively planning an hour slot in order to not rush the daily planning/positioning.

After the last rTMS session, follow-up neuropsychological testing, behavioral assessments, and fMRI will be performed.

At 30, 90 and 120 days post the last rTMS session, a selection of neuropsychological and behavioral assessments will be mailed to the patients for the subject to complete and mail back. These assessments may be done alternatively over the phone.

F) Actiwatch

Data will be collected using Actiwatch spectrum plus (hardware) over a period of up to 2 weeks from our subjects. This data will be stored in a computer and processed using Actigraph (software licensed from Philips Respironics). The equipment is off the shelf commercial products with FDA approvals.

The subject will wear Actiwatch on their wrist and perform regular activities: sleeping, sitting, running, walking, etc. After finishing data collection, the Actiwatch will be returned to the study staff. The study staff will use USB cord to download the data to computer with actigraph software. This assessment is optional.

G) Behavioral Assessments

A selection of the following assessments may be performed, either on paper, electronically or over the phone. Assessments include PRO-CTCAE and the PSQI Sleep Questionnaire. See details in file "Behavioral assessments.pdf". These assessments will require approximately 30-60 minutes.

9) Cost to Subjects

There is no monetary or financial cost incurred by participants who enroll in this trial. Participants will, however, be responsible for their own travel to the research laboratory. While the participants will not be reimbursed for travel, the research team will cover the cost of parking.

Though no other monetary/financial costs are affixed with participation in this trial, there is a **significant “time cost”** associated with completing this trial. Given the nature of this trial, we understand that this may place a burden on the participant's scheduling and whereabouts.

10) Risks to Subjects

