Repeated measures ANOVA will be employed. The independent variable is rTMS treatment. The primary outcome measure is cognitive function, and the secondary outcome measures is brain functional connectivity. Alpha = 0.05 will be used as the significance level for all analyses. Results will be corrected for multiple comparisons.

19) SCHEDULE OF EVENTS

Study stage	Baseline	Treatment Week #1		Treatment Week #2	Final Treatment	Follow-Up		
		Day 1	Day 2-5			Day 42 +/- 7	Day 102 +/- 25	Day 132 +/- 25
Study event	Day 0				Day 12			
Consent	X							
Neuropsychological testing	X				X	X	X	X
Behavioral testing	X				X	X	X	X
Urine Pregnancy test	X							
Structural MRI	X							
Functional MRI	X				X			
TMS treatment*		X	X	X	X			
Actiwatch ¹		X	X	X	X			
Frailty task		X			X			

*The TMS treatment sessions do not need to start immediately after Baseline.
¹Optional tasks, subjects can opt out this task.

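### Subjects are selected for low memory scores at the same single testing that serves as their only comparator, so a primary score drawn from the selecting tasks is biased towards improvement

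*Combined protocol and SAP*

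**What the plan says.** **Selection.** Section 6 applies cut-offs at the first appointment: "The first appointment will include the neuropsychiatric exams and pre-determined cut-offs (previously described) will be used to select appropriate subjects". It adds: "The selection is based on multiple neuropsychiatric tests". Section 5 (PCCI Diagnosis) gives the cut-offs: MMSE 24-27, MoCA 18-26, CDR 0.5, and a score "1 standard deviation below the mean for their age and education matched peers on normative data in at least 2 memory tasks". The memory tasks that count are not named.

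**Comparator.** Section 8 states: "Subjects will undergo testing at baseline prior to TMS treatments and once more at the end of the 2-week intervention". The Section 19 schedule has one neuropsychological testing before treatment, in the Day 0 column that also holds consent. Section 7 allows no procedure before consent. No screening test, run-in or second baseline is described.

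**Outcome and analysis.** Section 8B lists MMSE, CDR and the NACC UDS 3.0 battery (which includes MoCA) as measures of cognitive performance, with AVLT, NAART and Stroop in addition. Section 18 specifies a repeated measures ANOVA with rTMS as the independent variable, and says: "The primary outcome measure is cognitive function". It names no test.

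**Design.** "12 participants with PCCI will be recruited to participate in this trial", and all of them receive active stimulation. Section 2 calls the study a pilot that will test efficacy.

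**The concern.** A low score at one testing is part stable deficit and part chance error. Admitting only low scorers favours subjects whose error was negative that day. That error is not expected to recur at retest, so the group mean rises without any treatment effect.

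Here the same low score stays in the analysis as the comparator. With no control group, the ANOVA cannot separate this rise from an effect of rTMS. Correction for multiple comparisons lowers rejection rates but leaves the shifted mean in place. The later follow-ups do not help, because they are compared with the same Day 0 score.

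This bias is distinct from the lack of a control arm: it comes from the selection rule and can be reduced within a single-arm design. At stake are the reading of the primary outcome and any effect estimate carried into a later trial.

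**Working it through.** **The plan's own figures.** The documents give n=12 and alpha 0.05, but no effect size, SD, retest reliability or power, so there is no sample-size calculation to reproduce.

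**Inputs from the documents.** n=12; one testing before treatment; a one-sided cut at -1 SD on at least 2 memory tasks; alpha 0.05.

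**Assumed inputs.** Retest correlation r = 0.6-0.8; mean of the referred population mu = 0, -0.5 or -1 in norm SD units; true-score correlation between tasks 0.5; no treatment or practice effect; two-sided paired t test (sidedness is not stated); four candidate memory tasks, or exactly two.

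**Model.** Score = true score (variance r) + error (variance 1 - r). Expected change = -E[error at Day 0, given selection].

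**Closed form for one test with one cut (a check on the model only).** Expected gain = (1 - r) × φ(c)/Φ(c), with c = -1 - mu.
- mu = 0: φ(-1)/Φ(-1) = 0.2420/0.1587 = 1.525. Gain = 0.4 × 1.525 = 0.61 at r = 0.6, and 0.2 × 1.525 = 0.31 at r = 0.8.
- mu = -1: φ(0)/Φ(0) = 0.3989/0.5 = 0.798. Gain = 0.4 × 0.798 = 0.32 and 0.2 × 0.798 = 0.16.

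The protocol does not have this one-test rule. The rule it does have was simulated.

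| Rule and score analysed (errors independent) | Expected gain, SD | False positives (nominal 5%) |
|---|---|---|
| Any 2 of 4 tasks low; one fixed selecting task | 0.04-0.21 | 5-12% |
| Any 2 of 4 tasks low; composite of the selecting tasks | 0.04-0.21 | 7-33% |
| Exactly two tasks, both low; one of them | 0.13-0.49 | 10-47% |
| Test not used to select | about 0 | about 5% |

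The low ends are r = 0.8 with mu = -1; the high ends are r = 0.6 with mu = 0. The composite has the same mean gain as a single task but less noise, so it rejects more often. A wider pool dilutes the bias: with six tasks, one fixed task gains about 0.02-0.12 SD.

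**Shared error within a day.** A bad day can lower every test given that day. If half the error variance is shared (an assumption), under the 2-of-4 rule a test not used to select still gains 0.08-0.36 SD, with 7-26% false positives. In every scenario run it was less biased than the selecting tasks.

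**MMSE and MoCA.** Both are windows with a floor. With an assumed MoCA SD of 3 and r = 0.7-0.9, the 18-26 window yields a gain of about 0.1-0.6 points if the source mean is 24-26. If the mean is 22, the middle of the window ((18 + 26)/2 = 22), the gain is about zero.

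**The case against.** The strongest reply has four parts.

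1. **The large figures describe a rule the plan does not have.** A reader might infer from the one-test calculation that a false-positive rate of 36-65% is expected. That needs one test alone to select from a population at the norm. The plan requires at least two memory tasks among other criteria, and Section 6 refers patients because of symptoms and physician assessment, so their mean is probably already low. A reader might also point to each subject's two lowest tasks, which gain 0.11-0.64 SD (r 0.6-0.9, four or six tasks). Section 18 proposes no such analysis. This part stands: for one fixed task under the 2-of-4 rule the effect is modest.

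2. **MMSE and MoCA do not behave like the memory cut.** This stands. Their floors weaken the bias and may cancel it.

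3. **Changing the test does not cure the problem.** A reader might infer that tests not used to select are free of the bias. That is so only if errors are independent between tests on the same day. Nor do the documents show that AVLT is non-selecting: it is a memory task, and nothing excludes it from the eligibility count. Section 8C offers only a selection of tasks, and these have no row in the schedule. This limits the remedy but does not defeat it.

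4. **It is a pilot.** Section 8E speaks of acceptability and practicality, and Section 14 of feasibility. This lowers the severity. It does not dispose of the point, because Section 2 states an efficacy aim and Section 18 tests at 0.05.

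**Conclusion.** The concern holds in conditional form. The documents establish selection for low scores, one testing before treatment that is also the comparator, and a cognitive battery that contains selecting tests. If the primary score is drawn from the selecting memory tasks, its expected change is biased upward with an inert treatment. The one-sided memory rule drives this.

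The documents do not support the stronger statement that the primary result will show a false benefit. The primary test is not named, no reliability or referral mean is given, and the bias is a shift in expectation, not a certain significant result. Under the stated assumptions with independent errors it runs from negligible (0.04 SD, about 5% false positives for one fixed task of four) to serious (0.49 SD, 47% when exactly two tasks must both be low). Because the plan leaves the endpoint open, it does not rule out the worse cases.

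Severity: should-fix.

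**What to change.** **Section 5.** Name the NACC UDS memory tasks that decide eligibility, and state that AVLT, Stroop and the Section 8C tasks are not used for it.

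**Section 18.** Take the primary cognitive score from one named test in the existing battery that does not select, for example AVLT Delayed Recall, given on Day 0 and Day 12. Report change on the selecting tests as descriptive, with a note that it includes regression to the mean. Use a Section 8C task only if it is fixed in advance and scheduled on both days.

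**State the limit.** The change reduces the bias but does not remove it. Error shared across tests on the same day and practice effects remain, so change from baseline cannot by itself be attributed to rTMS.

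**Cost.** With AVLT, the change is wording only: no new test, visit or subject. A Section 8C task would need a schedule entry. The downside is that the tests most visibly impaired at entry become descriptive.

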PCCI is not surprisingly very difficult to study and is still not well understood including PCCI and MRI changes. We hope that this work including the MRI will add to the knowledge on PCCI but there is no specific MRI "signature". Diagnostic criteria for PCCI has been a topic of recent NIH RFA but it will likely be years before the publications come out from those grants.

2) Purpose

In this pilot study, we propose to test the efficacy of rTMS for the treatment of PCCI. Efficacy measures will include baseline and post-rTMS neuropsychological testing, functional MRI and biometry data using body worn sensors.

3) Lay Summary (approximately 400 words)

Transcranial magnetic stimulation (TMS) is a safe and non-invasive brain stimulation technique. It uses a magnetic coil to stimulate brain tissue painlessly using only a magnet (no electrodes or electrical wires) in a procedure that does not involve any surgery or sedation. TMS is currently FDA approved to treat depression and migraines. Although this technology is applicable to many other brain conditions as well, it has not been systematically examined in individuals with "Chemo-brain". Chemo-brain or Post-Chemotherapy Cognitive Impairment (PCCI) is defined as cognitive changes including impairment of memory, learning, concentration, reasoning, executive function, attention and visuo visio-spatial skills that occur during or after chemotherapy treatment.

In this study, we will:

- 1) use high-resolution magnetic resonance imaging (MRI) of individuals' brains to determine precisely where to place the TMS magnetic coil in order to stimulate the target brain region based off their unique brain structure.
- 2) use TMS to stimulate the target region of the brain.
- 3) take high-resolution MRI pictures of the brain both baseline and post-TMS to study whether the brain activity of the target region changes as a result of the TMS stimulation.
- 4) perform neuropsychological tasks baseline and post-TMS to study if performance is improved following stimulation of the target brain region.
- 5) collect data from completing Frailty assessments, baseline and post-TMS.
- 6) study the short-term and long-term treatment effects.
- 7) collect subject's daily activity and sleep/wake patterns from watch style device (<http://www.actigraphy.com/solutions/actiwatch/actiwatch-plus-specifications.html>).

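### Section 18 names only repeated measures ANOVA: if mailed follow-ups enter it, its default discards any subject with a missing form and the result can be biased; a mixed model would use all the data

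*Combined protocol and SAP*

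**What the plan says.** Section 18 gives the whole analysis in a few sentences. The method is "Repeated measures ANOVA will be employed" and the factor is described as "The independent variable is rTMS treatment". Then: "The primary outcome measure is cognitive function, and the secondary outcome measures is brain functional connectivity". The rest reads "Alpha = 0.05 will be used as the significance level for all analyses" and "Results will be corrected for multiple comparisons". It does not say which visits are levels of the factor, which form of ANOVA is meant, whether a sphericity correction applies, or what happens to a subject with a missing assessment.

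The schedule in Section 19 puts neuropsychological testing on Days 0, 12, 42 (±7), 102 (±25) and 132 (±25), and functional MRI on Days 0 and 12 only. For the three later visits, Section 8 E says "a selection of neuropsychological and behavioral assessments will be mailed to the patients for the subject to complete and mail back", with the telephone as an alternative. The Lay Summary (Section 3, item 6) lists as an activity "study the short-term and long-term treatment effects". On size, Section 5 says "12 participants with PCCI will be recruited to participate in this trial".

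**The concern.** The one named method has to serve the long-term aim, and three of the five cognitive assessments depend on remote return. Classical repeated measures ANOVA needs a complete row for each subject over the visits it includes. One unreturned form on Day 132 would by default also remove scores already obtained on Days 0 and 12. With 12 subjects that can cost a large share of the information. If return is related to how the subject responded, those who remain are a selected group, so even the Day 0 to Day 12 change can be distorted. Separately, the ordinary F test assumes sphericity. That may fail over gaps of 12, 30, 60 and 30 days if scores taken further apart are less correlated.

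**Working it through.** **Inputs from the documents.** N = 12, single arm (Section 5); cognition on Days 0, 12, 42, 102 and 132 (Section 19); three remote assessments (Section 8 E); alpha 0.05 (Section 18). There is no power, SD, return rate or dropout figure to reproduce. Return rates and covariances below are therefore assumptions, shown as ranges.

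**1. Complete cases.** With independent return probability p per form, expected n = 12 × p³. For example, 12 × 0.90³ = 12 × 0.729 = 8.7.

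**2. Width of the Day 0-12 interval, relative to all 12.**
- Paired contrast on completers: [t(n−1)/√n] ÷ [t(11)/√12]. At p = 0.90: (2.319/√8.748) ÷ (2.201/√12) = 0.784/0.635 = 1.23.
- ANOVA pooled error over five visits: [t(4(n−1))/√n] ÷ [t(44)/√12]. At p = 0.90: (2.040/√8.748) ÷ (2.015/√12) = 0.690/0.582 = 1.19.

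| Return per form (assumed) | Expected complete cases | Chance of 8 or fewer | Widening, pooled error | Widening, paired |
|---|---|---|---|---|
| 0.90 | 8.7 | 42% | 19% | 23% |
| 0.85 | 7.4 | 74% | 30% | 40% |
| 0.80 | 6.1 | 92% | 44% | 62% |
| 0.70 | 4.1 | 99.5% | 84% | 142% |

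For a paired contrast, the standardised change detectable with 80% power at two-sided 0.05 rises from 0.89 (n = 12) to 1.07 (n = 9) and 1.44 (n = 6).

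**3. Bias.** Suppose there is no true change and that return per form is 0.9 for subjects above the median Day 12 gain and 0.7 for the rest. The chances of being complete are 0.9³ = 0.729 and 0.7³ = 0.343. The mean of a half-normal is 0.798 SD, so the complete-case Day 12 change is 0.798 × (0.729 − 0.343)/(0.729 + 0.343) = +0.29 SD of change. The false 'improved' rate is about 12%, against a nominal 2.5%.

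The result depends on the assumption:
- The reverse pattern gives −0.29.
- 0.9 versus 0.85 gives 0.798 × (0.729 − 0.614)/(0.729 + 0.614) = +0.07.
- Equal return gives 0.

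For the Day 132 change, with a 20% base miss rate per visit, simulation gave +0.07 to +0.20 SD when missingness depended on the Day 0-12 change, and 0 to −0.25 SD when it depended on the Day 12 score.

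In the 0.9/0.7 scenario, maximum likelihood on all available data gave 0.00. Its empirical standard error was 0.288 against 0.385 for complete cases, about 25% smaller. Missingness there depended only on observed scores, so it was missing at random by construction.

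**4. Type I error of the uncorrected F(4, 44), n = 12, by simulation on the protocol's actual days.**
- Compound symmetry: about 5% (epsilon 1.00), whatever the spacing.
- Random intercept plus decaying correlation plus error: 6.0% (epsilon 0.84).
- Exponential decay, 30-day correlation 0.5 to 0.85: about 7% to 9% (epsilon 0.69 to 0.50).
- With Greenhouse-Geisser correction: 3.1% to 4.9% over all covariances tried.
- Two visits only: epsilon is 1 and the error 4.9%.

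Treating the five visits as equally spaced gives epsilon 0.81 to 0.60 for visit-to-visit correlation 0.5 to 0.85. Those values do not describe this schedule.

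**The case against.** The strongest reply is that the plan may never put follow-up visits into the ANOVA. The factor is treatment, not visit. Section 8 opens with one test before treatment and one at the end of the two weeks, and Sections 2 and 8 E define the efficacy measures as before and after rTMS. Only a selection of tests is repeated at follow-up, so many measures may have no five-visit series. On that reading sphericity does not arise and a missing form costs nothing at Day 12. This stands, and it always covers connectivity, which has two scans. It leaves the long-term aim with no analysis at all.

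Three stronger readings are tempting, and the documents do not support them:
- A reader might infer that the plan prescribes dropping subjects. It does not; deletion is the default of the classical method where no rule is given.
- A reader might infer that uneven spacing makes the F test over-reject. Spacing alone does not break sphericity, and a routine correction controls the error. Over-rejection by itself would not justify replacing the ANOVA.
- A reader might infer bias towards benefit. No document gives a return rate or says who fails to return forms, so neither size nor direction is known.

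There are mitigations. Telephone contact may raise return, withdrawn participants are asked to complete follow-up (Section 15), and recruitment aims at 12 completed subjects (Section 6). However, 'completed' is undefined, recruitment may end at about two years, and replacing subjects does not remove complete-case bias.

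**Conclusion.** The point holds conditionally. If any follow-up visit enters a classical repeated measures ANOVA, the default analysis loses subjects, can be biased in either direction, and can over-reject when sphericity fails. The loss is the firmest part: even at 90% return per form, about 8.7 of 12 subjects are expected to remain. It rests on assumed, independent return rates. The +0.29 SD is an illustration under one assumed pattern, and the 7-9% error rate needs correlation that decays with time and no correction. If the ANOVA is Day 0 versus Day 12 only, none of this applies, and the defect is instead that no long-term analysis is specified. The change should be made on either reading, because a better estimator is available for the same data.

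**What to change.** For measures collected at follow-up, replace the ANOVA sentence in Section 18 with text such as:

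*Each cognitive measure collected at follow-up will be analysed with a linear mixed model fitted by REML to all available data from every treated subject, with visit as a categorical fixed effect and Kenward-Roger degrees of freedom. The covariance will be heterogeneous compound symmetry; if the model does not converge, a random intercept will be used. The Day 0 to Day 12 change and each change from Day 0 to a follow-up visit will be reported with 95% confidence intervals. Validity rests on data being missing at random.*

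A spatial-power structure on actual assessment days, with the same fallback, is an alternative first choice; the sequence must be fixed before data are seen. An unstructured matrix over five visits has 5 × 6/2 = 15 parameters and is not a safe first choice with 12 subjects. Section 18 should also state which visits and measures enter the model. If the ANOVA is kept, the minimum is a Greenhouse-Geisser correction and a stated missing-data rule; the correction does nothing for lost subjects or bias.

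The cost is a short SAP amendment and standard software, with no new data or patients. The small downside is that results depend somewhat on the covariance structure at n = 12. The simulation in the working used plain maximum likelihood, so small-sample coverage of the REML model is not shown here.
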